This project will test the safety and effectiveness of long term (i.e. 12 weeks) administration of the injectable extended-release of naltrexone; Vivitrol[®]. Vivitrol[®] is primarily used in the management of alcohol and opioid dependence. Naltrexone maintenance (e.g. oral) seems a promising treatment for cannabis use disorder (CUD). Therefore, administering Vivitrol[®] may have therapeutic properties for treatment of cannabis use disorder. The data collected will be used to ensure that the administration schedule we have planned for the subsequent future randomized clinical trials is appropriate.

In this study we will focus on the tolerability and effectiveness of the antagonist at the μ -opioid receptor, Vivitrol[®], to reduce cannabis use, increase abstinence rates and reduce cannabis withdrawal and craving.

OVERVIEW

[figure not shown]
The study will be open label, with no placebo control. Ten male and female subjects seeking treatment for cannabis dependence subjects will undergo study procedures as outlined below. Treatment with Vivitrol[®] will start at day 1 (week 1) and a target quit date will be set up at Day 7 (but subjects will be allowed to stop using cannabis before if they are willing and able to). There will be a total of 12 weeks (3 injections, 1 every 4 weeks) of exposure to Vivitrol[®]. Study visits will occur weekly during the medication phase of the study. Motivational Enhancement Therapy and Cognitive Behavioral Therapy (MET/CBT) will also start at Week 1 and therefore, all participants will receive a combination of pharmacotherapy (Vivitrol[®] 4 mL intramuscular injection) associated with MET/CBT for 12-weeks in accordance with the intervention practices shown to be effective in treatment of cannabis dependence [54]. The intervention will be adapted from the Brief Counseling for Marijuana Dependence manual published by the Substance Abuse and Mental Health Services Administration (SAMHSA). In addition, to ensure compliance a Contingency Management plan will be implemented with \$5 voucher that will be provided at each visit that is attended and at which biological samples have been provided, but with 5\$ voucher loss for a missed appointment. The vouchers will be provided at end of treatment phase and at end of the follow-up phase.

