All subjects will receive a weekly MET/CBT session with a trained therapist. This is an adaptation of a nine-week MET/CBT intervention which has been previously studied for the treatment of cannabis dependence and has been found to be effective [54]. The intervention in the proposed study emphasizes the development of motivation for change and the implementation of skills to reduce and abstain from cannabis use, using the Brief Counseling for Marijuana Dependence manual published by the Substance Abuse and Mental Health Services Administration (SAMHSA). In this intervention, use of empathic therapeutic style helps resolve ambivalence, increase discrepancies about personal goals and cannabis use, and elicit motivation to change. Once ambivalence about cannabis use is addressed, the sessions focus on the cognitive, behavioral and emotional changes necessary for dealing with cannabis dependence while supplying coping strategies for predictable obstacles. As studies of psychosocial interventions in cannabis dependence have shown that more intensive interventions have a more sustainable outcome [54], the MET/CBT sessions in the proposed trial will continue for 12 weeks. The current SAMHSA manual provides an outline for this intervention for 9 weeks and provides 4 additional elective topics. In this study, participants will receive the 9 weekly sessions as outlined and then provided 3 of these elective topics for a total of 12 weeks. These elective topics will be identical amongst all participants. Addition of this intervention will allow for the necessary conditions to assess the additive value of treatment with Vivitrol® for cannabis use disorder.

We will seek participant's permission to audio record the MET/CBT sessions. A proportion of these audio recordings will be reviewed by a member of the research team to confirm that the assessment measures and the psychotherapy are provided according to standardized instructions [63-65]. MET/CBT may be conducted remotely by video call (i.e. Webex) if necessary. Remote therapy sessions will be conducted in accordance with the CAMH Research Guidelines for Virtual Participant Sessions.

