Our Primary outcome measures will be: 1) tolerability which will be assessed by determining the number of participants who withdraw from the study because of SAEs and 2) pilot efficacy of this intervention will be assessed by assessing seven-day point prevalence cannabis abstinence one week after the end of medication phase; and at 3 month follow up. Secondary outcome measures will be: 1) percentage of days of cannabis use over the study duration until the 3 month follow up; 2) amount of cannabis use over the study duration until the 3 month follow up; 3) effects on withdrawal symptoms scores, craving scores and number of urine samples screen as positive and 4) DSM5 criteria for CUD at the end of treatment and follow-up as compared with baseline. Efficacy analyses of count variables (e.g. number of joints per week) will be performed using generalized estimating equations (GEEs), specifying a negative-binomial distribution for the counts. Linear mixed models will be used to analyze continuous, secondary outcome measures (e.g. mood and anxiety ratings, physiological measures). All efficacy analyses will be by intention-to-treat. Treatment week will measure changes within-subjects. Subjects will be use as a measure of abstinence in this study. Urine samples will be collected and analyzed for THC metabolites.

Procedure for accounting for missing, unused, and spurious data: In the final report the procedures used to deal with missing, unused or spurious data in statistical analyses will be described.

Procedures for reporting deviations from the original statistical plan: Any deviation from the planned statistical analyses will be described in the final report.

Power calculation: The goal is to collect pilot data to demonstrate tolerability and trend for efficacy of Vivitrol® for treatment of cannabis dependence. We are hypothesizing that the use of cannabis will decrease by at least 50% after treatment with Vivitrol®. Assuming Cannabis use of around 9.5 g (SD = 5) at baseline [as per paper], a sample of 10 subjects will give us 80% power to detect a decrease in cannabis use of 50% from baseline to the last time point. The power calculation was conducted through Monte Carlo simulation, where 5000 replications were conducted. It was also assumed that the

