correlation between baseline and the last time point was 0.6. A Mixed Effect Model was adjusted for each replication, where Time was the only Fixed Effect and Subjects entered the model as Random Effects. The power in such simulation is defined as the proportion of the replications where the Time effect is significant at confidence level 0.05 and two tailed test. No dropout was assumed.

Termination of the Study

Reasons for withdrawing individual subjects from the study may include one or more of the following:

- 1) Severe side effects;
- 2) Major protocol deviation;
- 3) Subject lost to follow-up;
- 4) Withdrawal of consent;
- 5) Pregnancy

Any subject may be discontinued from the study at the discretion of the investigators if it is deemed to be in the best interest of the subject.

Study Documentation

Investigators will retain a subject identification code list if they need to contact subjects after the study. This list will contain the complete name, identification number, address and phone number of all subjects and will be held confidentially at the investigators site after completion of the study.

A CRF will be completed for each subject enrolled in the study. A subject screening log, noting reasons for screen failure, where applicable, will be maintained for all subjects. All information recorded on the CRFs for this study will be consistent with the subject's source documentation (e.g. medical records). The investigator will document the obtained informed consent and record all medication administration, medical history, results of laboratory tests and adverse events in the CRF. Laboratory printouts and psychometric assessments will be considered source documents and will be incorporated into the CRF without transcription in a confidential manner.

The data collected during the study will be typed or written onto the CRF and other study documents using a ballpoint pen. If an error is made, it will be crossed out with a single horizontal line, and the new information clearly recorded next to the error, initialed and dated. Correction fluid is not allowed at any time.

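### The plan says the additive value of Vivitrol can be assessed, but one uncontrolled arm with all treatments started in week 1 cannot separate Vivitrol's contribution from other causes of change

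*Combined protocol and SAP*

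**What the plan says.** Under Psychological support: MET/CBT intervention, the plan explains why everyone gets therapy: "Addition of this intervention will allow for the necessary conditions to assess the additive value of treatment" with Vivitrol for cannabis use disorder. The same section says that the nine-week therapy being adapted has already been found effective.

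The Power calculation opens with: "The goal is to collect pilot data to demonstrate tolerability and trend for efficacy of Vivitrol". The aim paragraphs just before the Overview use similar language: "This project will test the safety and effectiveness of long term (i.e. 12 weeks) administration" and "In this study we will focus on the tolerability and effectiveness of the antagonist".

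On design, the Overview states: "The study will be open label, with no placebo control". Vivitrol starts on Day 1, MET/CBT in Week 1, and the target quit date is Day 7. The Study Flow Schema lists one group of 10. Vouchers and prize draws at visits are available to all (Contingency Management).

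On analysis, the Data analysis section says "Treatment week will measure changes within-subjects". The power statement is "80% power to detect a decrease in cannabis use of 50% from baseline to the last time point", from a simulated mixed model "where Time was the only Fixed Effect and Subjects entered the model as Random Effects".

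**The concern.** Assessing what Vivitrol adds to MET/CBT requires some estimate of what happens with MET/CBT and without Vivitrol. The plan has no source for one. There is no MET/CBT-only group, no therapy run-in before the first injection, no staggered start and no external benchmark figure. Uniform therapy standardises the background, but that isolates the drug only if some participants go without it.

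What is at stake is how the result will be read. A fall in cannabis use could be carried into the later RCTs as early evidence that Vivitrol works, when the same fall could arise with no drug effect.

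**Working it through.** **1. What the design can identify.** Expected pre-post change is the sum of the Vivitrol effect, the MET/CBT effect, the quit-date effect, any effect of the incentives, and natural course with regression to the mean. The trial observes only the total. Every subject has every component, and the treatment components all begin within the first week. MET/CBT lasts 12 weeks and the three injections, one every 4 weeks, cover 3 × 4 = 12 weeks. The two therefore end together, and the follow-up phase does not separate them either. A model with Time or treatment week as its only explanatory term estimates the total.

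**2. The plan's own figure.** Inputs from the Power calculation: baseline mean 9.5 g, SD 5, a 50% fall, correlation 0.6, n = 10, two-sided 0.05, no dropout. Assumed here: SD 5 at the last time point too, and normal data. With two time points the model is equivalent to a paired t-test.

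- Difference: 9.5 × 0.50 = 4.75 g.
- SD of change: 5 × √(2 × (1 − 0.6)) = 4.472 g.
- Noncentrality at n = 10: 4.75 × √10 / 4.472 = 3.359. With 9 degrees of freedom the critical t is 2.262.
- Power: 84.7% at n = 10 and 79.6% at n = 9.

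So 10 is the smallest sample reaching 80% under these assumptions. The sample-size arithmetic is not in question.

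**3. The test cannot see the split.** Divide a 50% total fall between everything else and Vivitrol as 50/0, 25/25 or 0/50. The difference is 4.75 g each time, so the rejection probability is 84.7% each time.

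**4. Illustration with a Vivitrol effect of zero.** The documents give no figure for the fall expected without Vivitrol, so a range is assumed. Noncentrality is 9.5 × f × √n / 4.472, where f is the fall from all other causes.

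| Assumed fall f | Difference (g) | Chance of a significant Time effect, n = 10 |
|---|---|---|
| 10% | 0.95 | 9% |
| 20% | 1.90 | 23% |
| 30% | 2.85 | 44% |
| 40% | 3.80 | 67% |
| 50% | 4.75 | 85% |

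For f = 30%, the chance rises from 44% at n = 10 to 77% at n = 20 and 98% at n = 40. More subjects make the total change easier to detect and do nothing to apportion it.

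**5. Sensitivity to the end-point SD.** In general, SD of change = √(25 + s² − 6s), where s is the SD at the last time point. For f = 30% and n = 10, s = 2.5 gives an SD of change of 4.031 and a 51% chance; s = 6 gives 5.0 and 36%.

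**The case against.** The strongest reply is that the plan hides nothing. It says that it is open label and without placebo, that it is a pilot, and that its data serve to check the dosing schedule before later randomised trials. Tolerability is listed first among the primary outcomes, and efficacy is described as piloted. The therapy sentence speaks only of necessary conditions, and uniform background care is arguably one of them. This stands as mitigation: few readers would mistake the study for a controlled efficacy trial. It does not correct the two sentences. Conditions for assessing additive value include a group without the drug, and a trend credited to Vivitrol is still an attribution to Vivitrol.

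A second reply concerns the numbers. The size of the non-drug fall is assumed. The calculation follows the two-time-point power model on grams, a secondary outcome, whereas the plan also foresees negative-binomial GEEs for counts and mixed models over treatment weeks, and abstinence is the primary efficacy outcome. This stands too. The percentages are illustrative, and the identification argument needs none of them. That argument applies equally to the other within-subject analyses.

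A reader might go further and infer that the plan will declare Vivitrol effective if Time is significant, so that 44% is the trial's false-positive rate. The documents do not support that. The Time test defines power, and no success or go/no-go rule ties its p-value to a conclusion about Vivitrol.

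A reader might also think it enough to credit the effect to the combined treatment. That is unsupported as well, because an uncontrolled pre-post change includes natural course and regression to the mean.

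**Conclusion.** The point holds as a fault of attribution wording. The additive-value sentence claims a property that the design lacks, and the stated goal of showing a trend for efficacy of Vivitrol goes beyond what a single arm analysed over time can show. This follows from the design alone and holds at any sample size.

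The practical size cannot be fixed from the documents. With no Vivitrol effect and an assumed 30% fall from other causes, a significant Time effect appears in about 44% of trials at n = 10. This takes SD 5 at both times, correlation 0.6, normality and no dropout. Across assumed falls of 10% to 50% the figure runs from 9% to 85%.

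Nothing here shows that Vivitrol is ineffective, that N = 10 is wrong, or that this pilot must have a control arm. The tolerability and dosing-schedule aims are unaffected.

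**What to change.** 1. **Psychological support: MET/CBT intervention.** Replace the additive-value sentence with: *MET/CBT is given to all participants as standardised background treatment; this single-arm pilot does not estimate the additive value of Vivitrol, which is left to the subsequent RCTs.*
2. **Power calculation.** Replace the reference to a trend for efficacy of Vivitrol with: *uncontrolled pre-post change in cannabis use during treatment with Vivitrol, MET/CBT, a target quit date and contingency management.* Add: *No causal efficacy conclusion will be drawn for Vivitrol or for the combination, because natural course and regression to the mean are not controlled.*
3. **Aim paragraphs before the Overview.** Keep safety and tolerability of Vivitrol, and bring the two mentions of effectiveness into line with the wording in item 2.

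Leave N and the 80% figure unchanged. The cost is text only, with no extra subjects, visits or data. The downside is a more modest efficacy claim.

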Beck Depression Inventory-II (BDI-II), Hamilton Anxiety Scale (HAM-A), Hamilton Depression Rating Scale (HDRS), Brief Psychiatric Rating Scale (BPRS), Profile of Mood States, Drug Effects Questionnaire (DEQ), Addiction Research Center Inventory marijuana scale, St Mary's Hospital Sleep Questionnaire (SMHSQ)	X	X	X	X
SAFTEE	Х	Х	X (week 13 only)	X (end of trial)
ASI, World Health Organization Disability Assessment Schedule (WHODAS)	X	X (week 12 only)	X (week 13 only)	X (end of trial)
Urine for THC metabolite analysis	Х	Х	Х	Х
Vivitrol [®] administration		X (once every 4 weeks)		
MET/CBT		X		

Trial Objectives and Purpose:

Primary and Secondary Outcome Measures

Our primary outcome measures: 1) for tolerability will be the number of subjects that drop out because of SAEs and 2) for piloting efficacy will be the seven-day point prevalence cannabis abstinence at the end of medication phase and at the 3 month follow-up;

Secondary outcome measures will be 1) percentage of days of cannabis use over the study duration until the 3 month follow-up; 2) amount of cannabis use over the study duration until the 3 month follow up. 3) effects on withdrawal symptoms scores, craving scores and number of urine samples screen as positive.

Abstinence status will be also based on the urine samples collected during the trial.

PRELIMINARY RESULTS

A CUD treatment clinic has been set up at the Addiction Medicine Service (AMS)/Concurrent Outpatient Medical & Psychosocial Addiction Support Service (COMPASS) that is using the CBT-MET approach as standard of care. We have recruited subjects for pharmacotherapy trial for CUD at CAMH. Those preliminary results demonstrate the feasibility of recruiting the subjects for this study.

METHODS:

Subjects

Inclusion criteria

- Adult (18-64) male or female (gender to be analyzed as a covariate)
- Understand and willing to comply with study requirements and restrictions
- Willing to use appropriate contraceptive method throughout the study
- Otherwise healthy as judged by investigator based on medical history, physical exam, vitals, ECG and labs
- DSM 5 criteria for current CUD
- Report cannabis as primary drug of abuse
- Have cannabis positive urine drug screen
- Treatment seeking cannabis smoker

Exclusion criteria

- Meets DSM 5 diagnostic criteria for a current severe mental disorder, including substance-related and addictive disorders, other than CUD, tobacco use disorder, and caffeine-related disorders
- Unstable medical conditions

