Pharmacological Treatment: Vivitrol[®] 380 mg, 4 mL intramuscular injection Pilot Study in 10 subjects:

There is currently limited information to guide us on the Vivitrol[®] dosage to use in cannabis dependent individuals that likely have developed strong tolerance to cannabinoids. We are planning to administer Vivitrol[®] (380 mg, 4 mL intramuscular injection) every 4 weeks. Only eligible participants will be administered study medication (i.e. as per inclusion/exclusion criteria). On the day of the scheduled injection of Vivitrol[®] participants will be observed by qualified staff (i.e. staff performing injection) for 5-10 minutes for possible injection site reactions. Following injection of study medication the subjects will remain at CAMH facility for rest of study assessments (approx. 30 min to 1 h), so study staff will be able to monitor possible systemic AEs post-dosing. Medications and supportive measures will be available at CAMH clinic as per expected side effects of study medication. Additionally, participants in the study will be regularly assessed during the trial (see above schedule of assessments) for changes in health status, these assessments include ECG, vitals and CBC. The subjects in this study will be treatment-seekers that fit our inclusion/exclusion criteria and that will be treated open-label to ensure good tolerability. These 10 subjects will allow us to determine if our schedule for dosing is appropriate for the subsequent RCTs.

Biological sample collection (excludes samples used for general health assessments)

Urine samples will be collected weekly. All participants will have urine samples collected on the weekly visit. At any point that biological samples are taken, information about the last time the participant may have smoked cannabis and last used the study medication will be collected. All urine samples will be taken at the beginning of the visit to standardize the time. Each urine sample obtained will have creatinine measures and THC quantification determined by the CAMH laboratory. Appropriate temperature control until analysis will be maintained.

Biological sample collection for general health assessments

Urine and blood samples for general health assessments will be collected at Baseline and at the end of trial (see Summary of Study Assessments).

Psychological support: MET/CBT intervention

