All personal study participant data collected and processed for the purposes of this study will be managed by the investigators and their research staff with adequate precautions to ensure the confidentiality of this data, and in accordance with applicable national and local laws and regulations on personal data protection. Study data will be de-identified or coded. A master linking log with identifiers will be kept and stored separately from the data. The ethics committees approving this research and Health Canada will be granted direct access to the study participant's original medical records for verification of clinical trial procedures and/or data, without violating the confidentiality of the subjects, to the extent permitted by the law and regulations. In any presentations of the results of this study at meetings or in publications, the subject's identity will remain confidential.

Summary of risks and benefits to subjects:

Risks Associated with the Medication

Vivitrol® is a medication approved by the U.S. Food and Drug Administration for the treatment of alcohol and opioid dependence. Therefore, current evidence shows only the risks of using Vivitrol® associated with opioid and alcohol dependence. The risks of using Vivitrol® associated with cannabis use disorder are still unknown. Research staff and study physicians will be made aware of the serious adverse reactions that may be associated with Vivitrol® therapy in clinical use, which include: severe injection site reactions, eosinophilic pneumonia, serious allergic reactions, unintended precipitation of opioid withdrawal, accidental opioid overdose and depression and suicidality.

The adverse events seen most frequently in association with Vivitrol® therapy for alcohol dependence (i.e., those occurring in \geq 5% and at least twice as frequently with Vivitrol® than placebo) include nausea, vomiting, injection site reactions (including localized swelling, itching of the skin, nodules and swelling), muscle cramps, dizziness or syncope, somnolence or sedation, anorexia, decreased appetite or other appetite disorders.

The adverse events seen most frequently in association with Vivitrol® therapy in opioid-dependent patients (ie, those occurring in $\geq 2\%$ and at least twice as frequently with Vivitrol® than placebo) were hepatic enzyme abnormalities, injection site pain, nasopharyngitis, insomnia, and toothache.

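### The only planned tolerability outcome is withdrawal because of an SAE; stopping Vivitrol for a non-serious adverse event, adverse events overall and injections received are not counted

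*Combined protocol and SAP*

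**What the plan says.** Tolerability is the first of two primary outcomes in the combined protocol and SAP. Data analysis gives it as "tolerability which will be assessed by determining the number of participants who withdraw from the study because of SAEs". Primary and Secondary Outcome Measures says that the measure "for tolerability will be the number of subjects that drop out because of SAEs". The Data analysis text refers to leaving the study. The other section does not say whether dropping out means leaving treatment or leaving the study.

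The secondary outcomes cover days and amount of cannabis use, withdrawal and craving scores, and positive urine screens; Data analysis adds DSM-5 criteria for cannabis use disorder. The named models are GEEs for counts, such as joints per week, and linear mixed models for continuous measures, such as mood, anxiety and physiological measures. None of these counts adverse events, discontinuation of Vivitrol or injections received.

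The stated purpose is wider than this definition:

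- Study purpose, just before the Overview: "In this study we will focus on the tolerability and effectiveness of the antagonist".
- Power calculation: "The goal is to collect pilot data to demonstrate tolerability and trend for efficacy".
- Pharmacological Treatment: "These 10 subjects will allow us to determine if our schedule for dosing is appropriate for the subsequent RCTs". The planned course is "3 injections, 1 every 4 weeks" (Overview).
- Risks Associated with the Medication: the risks "associated with cannabis use disorder are still unknown".

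**The concern.** An event enters the primary tolerability count only if it is an SAE and also makes the subject leave. Two kinds of intolerance fall outside.

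**(a) Stops for non-serious events.** Risks Associated with the Medication lists the serious reactions separately from the events seen most often in alcohol dependence, which include "nausea, vomiting, injection site reactions (including localized swelling, itching of the skin, nodules and swelling), muscle cramps, dizziness or syncope, somnolence or sedation". A subject who declines the second injection because of one of these is counted only if the event also qualifies as an SAE.

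**(b) Stopping the drug but staying in the study.** Under the Data analysis wording such a subject is not counted, even if the cause was an SAE. The plan does not address this case, although the Hepatotoxicity paragraph treats continued dosing as a judgement of its own.

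Termination of the Study adds a third term by listing severe side effects as a reason for withdrawing a subject. Severe is not the same as serious, so a subject can be withdrawn under the study's own criteria for a side effect that its tolerability outcome leaves out.

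At stake is whether the pilot answers its own question. No planned outcome reports how many subjects completed the injection schedule that the study is meant to test.

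**Working it through.** **The plan's figure.** There is none for tolerability. The sample size of 10 was set on the change in cannabis use and has no bearing on this point.

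**Inputs.** From the documents: n = 10. Assumed, because the documents give no rates: r, the probability that a subject stops for any adverse event (10%, 20%, 30%), and s, the share of those stops that are SAE withdrawals (10%, 25%, 50%). Subjects are treated as independent.

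**Formulas.**

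- P(no SAE withdrawal) = (1 − rs)^10
- P(no stop at all) = (1 − r)^10
- P(reads 0/10 with at least one stop) = (1 − rs)^10 − (1 − r)^10
- P(reads 0/10 with exactly one stop) = 10·r(1 − s)·(1 − r)^9; subtracting this from the previous line gives the probability for at least two stops
- Expected stops not counted = 10·r(1 − s)

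**Worked case, r = 0.20 and s = 0.25.**

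- rs = 0.05, so (0.95)^10 = 0.599; (0.80)^10 = 0.107
- At least one stop: 0.599 − 0.107 = 0.491 (from unrounded values)
- Exactly one stop: 10 × 0.15 × (0.80)^9 = 1.5 × 0.134 = 0.201
- At least two stops: 0.491 − 0.201 = 0.290
- Expected uncounted stops: 10 × 0.20 × 0.75 = 1.5

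**All cases.**

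| s | r | 0/10 with ≥1 stop | 0/10 with ≥2 stops | Expected uncounted stops |
|---|---|---|---|---|
| 10% | 10% | 0.556 | 0.207 | 0.90 |
| 10% | 20% | 0.710 | 0.468 | 1.80 |
| 10% | 30% | 0.709 | 0.600 | 2.70 |
| 25% | 10% | 0.428 | 0.137 | 0.75 |
| 25% | 20% | 0.491 | 0.290 | 1.50 |
| 25% | 30% | 0.430 | 0.340 | 2.25 |
| 50% | 10% | 0.250 | 0.056 | 0.50 |
| 50% | 20% | 0.241 | 0.107 | 1.00 |
| 50% | 30% | 0.169 | 0.108 | 1.50 |

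**Precision, a separate matter.** The exact (Clopper-Pearson) two-sided 95% upper limit for 0/10 is 1 − 0.025^(1/10) = 0.308. This follows from n = 10 and would hold under any definition of tolerability.

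**The case against.** The strongest reply is that nothing is lost. SAFTEE is scheduled weekly in weeks 1 to 12 (Summary of Study Assessments). Medication administration and adverse events go into the CRF (Study Documentation). Every adverse event is assessed and reviewed (Adverse Events Reporting), and liver tests and blood counts precede the second and third injections. Adverse event and exposure tables could be built from these in any final report, and no threshold or go/no-go rule depends on the SAE count. The plan does not say that the dosing schedule will be judged from that count alone. The planned mixed models for mood touch one safety domain, since depression is among the listed serious reactions. The rates used above are assumed, and the protocol itself describes nausea as usually mild and brief.

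Much of this stands, and it limits the point to the planned outcomes and analysis; data collection is adequate. It does not remove the point. SAFTEE and the adverse event records are described as monitoring and record-keeping, with no commitment to analyse them. Models of mood scores do not count stops or injections. In an open-label, single-arm study, the choice of safety summary to set beside the primary count would otherwise be made after the results are known.

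Two narrower objections are fair. Receipt of all three injections mixes intolerance with loss to follow-up and withdrawn consent, so it should be read as exposure beside the adverse-event count. And a list of withdrawal reasons need not use the same term as an outcome, so the severe/serious difference mainly illustrates gap (a).

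**Conclusion.** The concern holds. Followed as written, the primary tolerability outcome can read 0/10 although subjects stopped Vivitrol because of side effects. Over the assumed ranges, the chance of a 0/10 reading with at least one such stop runs from 17% to 71%, and with at least two from 6% to 60%. The endpoint would miss 0.5 to 2.7 stops among 10 subjects on average. These figures illustrate the gap and do not predict what will happen, because r and s are not in the documents. The textual finding does not depend on them.

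The consequence is a weak and possibly over-favourable account of tolerability in a population whose risks the protocol calls unknown. No formal decision would be wrong as a result. It should be fixed, because a stated primary outcome is too narrow for the study's own question and the remedy uses data already planned.

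**What to change.** In Primary and Secondary Outcome Measures and in Data analysis, keep the SAE-withdrawal count and word it the same way in both, stating whether it means leaving treatment or leaving the study. Prespecify beside it, as descriptive tolerability outcomes:

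1. The number and proportion of injected subjects who discontinue Vivitrol, miss a scheduled injection or withdraw because of any adverse event. Count each subject once, give an exact (Clopper-Pearson) 95% confidence interval, and list stops with an unknown reason separately.
2. The proportion of injected subjects who receive all three injections. This needs no attribution of cause.
3. Adverse events by seriousness and severity, from the SAFTEE, adverse event and medication-administration records.

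State that 0/10 is compatible with a true rate of up to 30.8%. Reconcile the terms SAE and severe side effects by saying how a withdrawal for a severe but non-serious effect is counted, leaving the withdrawal criteria unchanged.

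The cost is low: added wording in two sections and a check that the CRF, which is not among the documents, records the reason for a missed injection. No extra visits, tests or subjects are needed. There are two downsides: tolerability may look less favourable, and attributing a missed injection to an adverse event needs investigator judgement.
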